## 2. Glossary

[figure not shown]
Term	Definition
ADE	Adverse Device Effect
AE	Adverse Event
ADHD	Attention Deficit Hyperactivity Disorder
ATRF	Antidepressant Treatment Resistance Form
ATIF	Antidepressant Treatment Intolerance Form
C-SSRS	Columbia – Suicide Severity Rating Scale
CAPA	Corrective and Preventive Action
CFR	Code of Federal Regulation
CGI-S	Clinical Global Impression scales - Severity
CGI-I	Clinical Global Impression scales – Improvement
CIP	Clinical Investigation Plan
CP	Conditional Power
CRF	Case Report Form
EC	Ethics Committee
DBS	Deep Brain Stimulation
DSM-V	Diagnostic and Statistical Manual of Mental Disorders- V
eCRF	Electronic Case Report Form
eCOT-NS	external Combined Occipital and Trigeminal Nerve Stimulation
ECT	Electroconvulsive Therapy
EDC	Electronic Data Capture
EOS	End of Study
FDA	Food and Drug Administration
HDRS	Hamilton Depression Rating Scale
IEC	International Electrotechnical Commission
IRB	Institutional Review Board
ISO	International Organization of Standardization
ITL	Israel Testing Laboratories
ITT	Intent to Treat
MBS	Most Bothersome Symptom
MDD	Major Depressive Disorder
MDRS/MADRS	Montgomery-Asberg Depression Rating Score
mITT	modified Intent to Treat
MOH	Ministry of Health
NSR	Non-Significant Risk
OCD	Obsessive Compulsive Disorder
ONS	Occipital Nerve Stimulation
OUS	Outside United States
P/N	Part Number
PNS	Peripheral Nerve Stimulation
PTSD	Post-Traumatic Stress
QIDS	Quick Inventory of Depressive Symptomatology

Term	Definition
Q-LES-Q	Quality of Life Enjoyment and Satisfaction Questionnaire
RDC	Remote Data Capture
SADE	Serious Adverse Device Effect
SAE	Serious Adverse Event
SCID	Structured Clinical Interview for DSM-V
TENS	Transcutaneous Electrical Nerve Stimulation
TMS	Transcranial Magnetic Stimulation
TNS	Trigeminal Nerve Stimulation
UM	User Manual
US	United States
U(S)ADE	Unanticipated (Serious) Adverse Device Effect
VAS	Visual Analogue Scale

### 3. Synopsis

Title	The MOOD study - Safety and efficacy of external Combined Occipital and Trigeminal Nerve Stimulation (eCOT-NS) for the treatment of Major Depressive Disorder (MDD)
Clinical Study Type	Pivotal, Pre-market, Non-Significant Risk (NSR) Device Study
Product Name	Relivion®DP (Device version PLV3; SW version 0.1.0.2; App Version 1.2)
Sponsor	Neurolief Ltd.
Indication under investigation	The Relivion® DP external Combined Occipital and Trigeminal Nerve Stimulator (eCOT-NS) is intended as an adjunctive treatment to pharmaceutical management of Major Depressive Disorder (MDD) in adults who failed to achieve satisfactory improvement from previous Antidepressant medication treatment. The Relivion® DP is a prescription device for patient at home, self-use.
Investigation Purpose	The MOOD Study will evaluate the safety and efficacy of a self-administered treatment for MDD using an external combined occipital and trigeminal nerve stimulator (Relivion® DP ). This pivotal clinical investigation is intended to support future marketing applications (US FDA and CE) for Neurolief's Relivion® DP device.
Product Status	Pre-market
Patient Population	Male and female; 18 – 70 years of age; Primary diagnosis by the DSM-V criteria for MDD
Primary Objectives	To assess the change in depressive symptoms, from baseline to 8 weeks post treatment initiation when using active external combined occipital and trigeminal nerve stimulation (Relivion® DP ), compared to sham stimulation (Relivion® DP -Sham), in subjects suffering from MDD. Depressive symptoms severity will be assessed by the HDRS17 depression scale total score.
Secondary Objectives	
 
To assess the proportion of subjects achieving at least 50% improvement ("responders") in the HDRS17 score from baseline to 8 weeks post treatment initiation when using the Relivion®DP device compared to sham stimulation (Relivion®DP-Sham), in subjects suffering from MDD.
 
To assess the proportion of subjects achieving remission (HDRS17 score ≤7) at the 8 weeks post treatment initiation when using the Relivion®DP device compared to sham stimulation (Relivion®DP-Sham), in subjects suffering from MDD.
 
To assess the change in depressive symptoms, from baseline to 8 weeks post treatment initiation when using the Relivion®DP device compared to sham stimulation (Relivion®DP-Sham), in subjects suffering from MDD. Depressive symptoms severity will be assessed by the MADRS depression scale total score.
 

Safety Objective	To demonstrate the safety of the Relivion® DP device in subjects suffering from Major Depressive Disorder (MDD).

Exploratory Objectives	
 
• To assess the change on the Clinical Global Impression (CGI) scale for Improvement (CGI-I) and change on the CGI-Severity scale (CGI-S) from baseline to 8 weeks post treatment initiation when using the Relivion®DP device compared to sham stimulation (Relivion®DP-Sham), in subjects suffering from MDD.
 
• To assess the changes in total score on the 16-Item Quick Inventory of Depressive Symptomatology Self-Rated (QIDS-SR-16) score from baseline to 8 weeks post treatment initiation when using the Relivion®DP device compared to sham stimulation (Relivion®DP-Sham), in subjects suffering from MDD.
 
• To assess the change in depressive symptoms from baseline to 8 weeks post treatment initiation when using the Relivion®DP device compared to sham stimulation (Relivion®DP-Sham) in subjects suffering from MDD. Depressive symptoms severity will be assessed by the HDRS21 depression scale total score.
 

Planned Study Duration	
Each subject will participate in the study for up to 20 weeks (including the screening period).
 
The duration of the treatment protocol for each subject will be 8±1 weeks of a double blind active or sham treatment phase, followed by 8±1 weeks of an active open label treatment. The overall enrollment period is expected to last approximately 18 months.

Study Design	
This is a prospective, multi-center, 2-arm randomized, parallel group, double-blind sham-controlled study followed by an open label active treatment phase.

	
The study will include the following study visits & phases:
 
 
• Visit 1- Screening (Day (-14)-0) - Screening & Preliminary Eligibility Assessment.
 
• Visit 2- Baseline (Day (-4)-0) – Eligibility, baseline assessment, Randomization to Relivion®DP vs. Sham control (1:1 randomization) and training.
 
• Double blind phase (Day 0 to day 56±7)- 5-7 days a week treatment: Active/Sham treatment protocol.
 
• Visit 3- Follow Up Visit (day 28±7)- MDD assessment.
 
• Visit 4- End of Double-Blind phase (day 56±7)- MDD assessment.
 
• Open label phase– Active treatment period: According to HDRS response in DB phase, in between Maintenance treatment 3-4 times a week and up to 5-7 days a week of intensified treatment (Day 56±7 to day 112±7)
 
• Visit 5- follow up visit (day 84±7) - MDD assessment.
 
• Visit 6- End of study (day 112±7)- MDD assessment and end of study.
 
 
After completion of the open label period the subject's participation in the study will be over.

Randomization	
Eligible subjects will be randomly allocated (with a 1:1 ratio) to one of the following 2 treatment groups based on a randomization scheme using the permuted block method stratified by center:
 
 
• Active stimulation
 
• Sham stimulation
 
 
The randomization scheme will be prepared by the study statistician using the SAS (version 9.4.) random number procedure. The block size will be random, and all study personnel will be therefore blinded to the randomization block size.

Sample Size	
The overall calculated sample size is up to 124 randomized subjects aged 22-70 to allow for 53 evaluable subjects per treatment group, anticipating a 15% drop-out, plus an additional up to 36 randomized subjects aged 18-21 to allow 15 evaluable subjects per treatment group. The study will follow a sample size adaptive design with one interim analysis planned to allow for sample size increase, completion per original sample size, stop for futility or stop for efficacy. One interim analysis is planned after 86 (~80% of the calculated adult sample size) evaluable subjects have been accrued.

Inclusion Criteria	
 
1. Males and females 18-70 years of age:           
 
a. Up to 124 randomized subjects aged 22-70
 
b. Up to 36 randomized subjects aged 18-21
 
 
 
2. Primary diagnosis of unipolar major depressive disorder by DSM-V criteria.
 
3. Current MDD episode lasts up to three years.
 
4. Score on the Hamilton Depression Rating Scale (HDRS21) <math>\geq 20</math>
 

	
 
5. Symptoms of current major depressive episode that, as determined by the Investigator, for the current episode and according to the Antidepressant Treatment Resistance Form (ATRF) or Antidepressant Treatment Intolerance Form (ATIF):           
 
• Did not respond or have insufficiently responded by less than 50% improvement; dose and duration defined & rated at minimum confidence level 3 on the ATRF;
 
• Did not respond or has insufficiently responded to at least one but no more than four adequate trials of antidepressant medications (<math>4 \geq \text{ATRF} \geq 1</math>) or
 
• Did not respond or has insufficiently responded due to poor tolerability to at least two inadequate antidepressant medication trials (<math>\text{ATIF} \geq 2</math>).
 
 
 
6. Subject must be on at least one (1) antidepressant medication (minimum therapeutic dose not required if tolerability precluded further dose titration) and is willing to remain on the same daily dose of antidepressant medication(s) for a minimum of 28 days prior to randomization and thereafter for the duration of the study.
 
7. For subjects receiving current depression focused psychotherapy: psychotherapy initiated at least 1 month prior to baseline visit with a stable frequency of visits regimen, in the opinion of the Investigator.
 
8. Subject is able to provide written Informed Consent and is capable of complying with the specified study requirements, as determined by the Investigator.
 
9. Subject has cognitive and/or motor skills needed to operate a smartphone and can be contacted by phone, as determined by the Investigator.
 

Exclusion Criteria	
 
1. History of intracranial surgery.
 
2. Current denervation in one or more of the following: the supraorbital or supratrochlear branches of the trigeminal nerve, or the greater occipital branch of the occipital nerve.
 
3. An implanted neurostimulators or any implanted metallic or electronic device in the head, a cardiac pacemaker or an implanted or wearable defibrillator, except for dental implants.
 
4. Skin lesion, scars, or inflammation at the region of the stimulating electrodes.
 
5. Subjects with a history of traumatic brain injury (TBI), defined as a disruption in the normal function of the brain that can be caused by a bump, blow, or jolt to the head, or penetrating head injury, within 3 months of study enrollment.
 
6. Pregnancy or Lactation.
 
7. Women of reproductive age not using a reliable contraceptive method as determined by the Investigator.
 
8. In the opinion of the Investigator, subjects with a psychiatric history consistent with, suspicious for, or diagnostic of, bipolar depression or depression associated with psychosis.
 
9. Borderline personality disorder, defined by DSM-V criteria, that in the judgement of the Investigator is likely to complicate the assessment of clinical response to study treatments or limits the patient's ability to comply with study procedures.
 

	
 
10. Subjects who, within one (1) year of study enrollment, have a history consistent with, suspicious for or diagnostic of, any of the following: psychosis, psychotic disorder, schizophrenia or schizoaffective disorder, in the opinion of the Investigator.
 
11. Subjects who demonstrate or have a history of any cognitive disorder or impairment, memory loss, dementia, confusion or delirium that, in the opinion of the Investigator, may compromise the integrity of the study data or impact the ability of the subject to comply with the study requirements.
 
12. Past 12 months active suicidal intent or plan as defined by a “yes” answer to Q4 or Q5 on the Columbia-Suicide Severity Rating Scale, (C-SSRS) or with a history of suicide attempt in the past twelve months.
 
13. Subjects currently (past month) meeting diagnostic criteria for Obsessive-Compulsive Disorder or post-traumatic stress disorder and that is their primary diagnosis.
 
14. Subjects meeting the DSM-V criteria for alcohol use disorder or other substance use disorder (not including tobacco/nicotine) within six (6) months prior to study enrollment.
 
15. The subject has any past or present medical condition, disease, illness, disorder or injury that, in the opinion of the Investigator, may reduce or hinder the subject’s ability to fully comply with all study requirements for the duration of the study or may confound the integrity of the study data.
 
16. Participation in a previous study with the Relivion®DP or the Relivion® device.
 
17. Treatment with Transcranial Magnetic Stimulation (TMS) in the past 6 months.
 
18. Current treatment with any other approved or investigational brain stimulation therapies (i.e. Vagus or trigeminal nerve Stimulation, tDCS, TES).
 
19. Failure to receive clinical benefit from an adequate trial of ECT in the current or a past depressive episode in the opinion of the Investigator.
 
20. Subject having received Botox treatment in the head or neck region within 90 days prior to study enrollment.
 
21. Subject having received supraorbital or occipital nerve blocks within 1 month prior to enrollment.
 
22. Head circumference smaller than 51 centimeters or larger than 60 centimeters.
 
23. Current neurological condition or disease which, in the opinion of the investigator, is likely to manifest a depressive syndrome or symptoms that would substantially confound the diagnosis or serial assessment of major depressive disorder.
 
24. Subjects participating in other clinical trials evaluating experimental treatments or procedures.
 

Primary Efficacy Endpoint	Mean change in depressive symptoms, measured by HDRS17 total score, from baseline to week-8 post treatment initiation.

Secondary Efficacy Endpoints	
 
Proportion of responder subjects- defined as the percent of subjects achieving at least 50% reduction from baseline in their HDRS17 total score, 8 weeks post Relivion®DP treatment initiation.
 
Proportion of subjects achieving remission- defined as the percent of subjects with HDRS17 score≤7 at 8 weeks post Relivion®DP treatment initiation.
 
Mean change in depressive symptoms, measured by MADRS total score, from baseline to week-8 post treatment initiation.
 

Safety Endpoint	Safety of the study device following study treatment: Incidence of adverse events and serious adverse events related or unrelated to the study device [Time Frame: up to 18 weeks post treatment initiation].
Exploratory Endpoints	
 
Mean Change in the severity and improvement scores - Clinical Global Impression scales (CGI-S and CGI-I) at 8 weeks post treatment initiation.
 
Mean Change from baseline in total score of the Quick Inventory of Depressive Symptomatology self-rated (QIDS-SR-16) score at 8 weeks post treatment initiation.
 
Mean change in depressive symptoms, measured by HDRS21 total score, from baseline to week-8 post Relivion®DP treatment initiation.
 

Statistical Considerations	
Study Hypothesis:
 
Null hypothesis: Mean change from baseline in HDRS17 to 8 weeks post treatment initiation in subjects suffering from Major Depressive Disorder (MDD) in the active Relivion®DP arm = Mean change from baseline in HDRS17 to 8 weeks post treatment initiation in the sham arm.
 
Alternative hypothesis: Mean change from baseline in HDRS17 to 8 weeks post treatment initiation in subjects suffering from Major Depressive Disorder (MDD) in the active Relivion®DP arm ≠ Mean change from baseline in HDRS17 to 8 weeks post treatment initiation in the sham arm.
 
Statistical Analysis:
 
Study Analysis Sets
 
Each of the following analysis sets will be evaluated for the principal statistical analysis:
 
Intent-to-treat Analysis Set (ITT)
 
The intent-to-treat (ITT) population will include all subjects enrolled in the study, aged 22 to 70, as randomized. This population will include all subjects who receive at least one active/sham treatment. According to the ITT principle all subjects will be analyzed in the treatment group as assigned by randomization.
 
Modified Intent-to-treat Analysis Set (mITT)
 
The modified intent-to-treat (mITT) population will include all subjects from the ITT set enrolled in the study, who completed the minimal stimulation time required by the protocol and have no post randomization exclusion criteria. The mITT analysis set will be analyzed in the treatment group as treated.
 
Per-Protocol Analysis set (PP)
 
All subjects from mITT set that complete the 8-week treatment period (without withdrawal) and without any major protocol deviations.
 
Modified Younger Intent-to-Treat (mYITT) Analysis Set
 
The modified younger intent-to-treat (mYITT) population will include all subjects from the ITT set enrolled in the study including subjects aged 18-21, who completed the minimal

stimulation time required by the protocol and have no post randomization exclusion criteria. The mYITT analysis set will be analyzed in the treatment group as treated.

**Statistical Analysis of Cohorts Analysis Sets**

Safety assessments will be performed on the ITT and mYITT analysis sets.

The mITT cohort will serve as the principal data analysis set for the primary and secondary statistical efficacy endpoints. The primary, secondary and exploratory efficacy assessment will also be performed on the per protocol (PP) analysis set for descriptive purposes and to show consistency of study results. Primary and secondary efficacy analysis will be performed on the mYITT set as well.

**Interim Analysis**

An interim analysis will be performed by an independent statistician once about 80% of the required number of subjects aged 22-70 have been randomized and completed the 8-week post treatment initiation visit.

Depending on the outcome of the interim analysis, the study will either continue to the originally planned sample size, stop for futility, stop for efficacy, or continue with an increased sample size. These decisions will be made based on the conditional power (CP), which is defined as the conditional probability that the result will exceed a critical value at the interim given the observed effect size.

Note that the interim analysis will be conducted on all populations (ITT, mITT, PP and mYITT analysis sets), and the study will be stopped due to futility only if the interim effects in all populations fall below the threshold.

**Handling of the Type I Error**

The overall significance level for this study is 5% using two-tailed tests, except for treatment by site interaction that will be tested at a significance level of 10%.

**Controlling the Overall Type I Error:**

The hierarchy approach will be adopted for the primary and secondary endpoints to control type I error due to multiple endpoint testing. It is recognized that the ordering is important only with regard to rejection or non-rejection of the null hypothesis. Thus, the first endpoint will first be analyzed and only if  $p \leq 0.05$ , will the second endpoint be analyzed, and so on.

**General**

Data will be analyzed using SAS ® version 9.4 or higher (SAS Institute, Cary North Carolina). All statistical tests will be two-sided.

Study data will be summarized with descriptive statistics and presented in tables and figures. Continuous variables will be summarized by a mean, standard deviation, minimum, median and maximum and categorical variables by a count and percentage. For comparison of means (continuous variables), the two-sample t-test or the Wilcoxon rank sum test will be used as appropriate. For comparison of proportions (categorical variables), the chi-squared test or Fisher's exact test will be used as appropriate. If multiple measurements are taken in a single subject, statistics described below will be appropriately modified to accommodate the within subject correlation.

**Primary Endpoint Analysis**

The primary efficacy endpoint is the change from baseline to 8 weeks post treatment initiation in HDRS17 score.

The change in HDRS17 from baseline to 8 weeks post treatment initiation will be compared between the treatment groups using a repeated measures analysis of covariance (ANCOVA, SAS® MIXED procedure). The model will include the following fixed effects: treatment group, visit, treatment group by visit interaction with Baseline HDRS17 and center entered as covariates. Baseline HDRS17 scores will be entered as a continuous variable so that the potential for co-linearity problems will be minimized. The treatment group by center will be evaluated as well, but not as part of the principal statistical evaluation. Additionally, the center variable will be grouped by country as US versus out of US (OUS) and the analyses for center will be repeated on this new variable.

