### **9.1.4. Visit 3 – 4 weeks Follow up (Day 28±7)**

Written below are the assessments to be completed at Visit 3 (either on site or remotely):

- Depression symptoms questionnaires:

- By site qualified rater: HDRS21 (HDRS17- removing 4 last questions from the HDRS21), MDRS, CGI-S & CGI-I
- By subject: QIDS-SR-16. Subject self-reported questionnaire may be filled in electronically (ePRO) or by hard copy.
- Suicidal intent assessment by the investigator team (C-SSRS)
- Change in concomitant medications, if any.
- Significant change in health status, if any.
- Adverse events will be documented.

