We use conservative estimates of a 3.3-point difference with a standard deviation of 6 points. Calculations show that a sample size of 53 subjects per group (total 106) would provide 80% power at a 5% level of significance (two-sided) to detect the difference between treatment and sham groups.

Given our preliminary results, together with other companies clinically relevant data, we hypothesize that our statistical assumptions are aligned with competitive treatments for MDD.

The company anticipates that after randomization, but before the endpoint can be observed, up to 15% of the subjects will drop out from the study irrespective of study arm and success of treatment; thus, an adjustment for this drop-out rate is made and a sample size of 124 is required at the point of randomization.

We shall randomize an additional up to 36 subjects (30+15% dropout) in the age range 18-21 to assess efficacy in this age range as well.

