1. INTRODUCTION

This Statistical Analysis Plan (SAP) is a more detailed companion to the Statistical Methods section of the study titled “The MOOD study – external Combined Occipital and Trigeminal Nerve Stimulation (eCOT-NS) for the treatment of Major Depressive Disorder (MDD)” and provides a comprehensive description of the analysis sets, endpoints, methods, and data analyses to be used. This SAP prevails when differences exist in descriptions or explanations provided in the protocol and the SAP. We shall address analysis strategies for the open label stage of the study. Addressed as well is a plan for prognostic factor analysis to identify potential baseline parameters related to the primary endpoint and its derivatives.

Relivion®DP, an external Combined Occipital and Trigeminal Afferent Stimulation (eCOT-AS) is proposed as a novel treatment for MDD. The combination of neuromodulation of both the occipital and the trigeminal nerve branches non-invasively is made possible for the first time, after having been successfully performed either separately or in invasive procedures.

Major depressive disorder is one of the leading causes of disability worldwide. However, treatment options are still limited, therefore new approaches are needed to enhance clinical improvement. The non-invasive combined neuromodulation of both the occipital and trigeminal nerve branches is a safe, self-administered novel technology with high potential for treating MDD patients. Based on this rationale, Neurorelief developed the Relivion®DP, a neuro-stimulator applying combined occipital and trigeminal afferent stimulation for treatment of major depressive disorder (MDD). Following completion of an early clinical study showing promising results, Neurorelief designed the proposed clinical trial to evaluate the safety and efficacy of the Relivion®DP in a two-arms controlled, double blinded randomized study.

The MOOD Study will evaluate the safety and efficacy of a self-administered treatment for MDD using an external combined occipital and trigeminal afferent stimulator (Relivion®DP).

This pivotal clinical investigation is intended to support future marketing applications (US FDA and CE) for Neurorelief’s Relivion®DP device.

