11.5 Endpoints Analyses

11.5.1 Primary Efficacy Endpoint Analyses

The primary efficacy endpoint is the change from baseline to 8 weeks post treatment initiation in HDRS-17 score.

The change in HDRS-17 from baseline to 8 weeks post treatment initiation will be compared between the treatment groups using a repeated measures analysis of covariance (ANCOVA, SAS® MIXED procedure). The model will include the following fixed effects: treatment group, visit, treatment group by visit interaction

with Baseline HDRS-17, and center entered as covariates. If covariates are identified in the prognostic factor analysis, they may be added to the model as well. Baseline HDRS-17 scores will be entered as a continuous variable so that the potential for co-linearity problems will be minimized. The treatment group by center interaction will be evaluated as well, but not as part of the principal statistical evaluation.

The unstructured covariance matrix structure will be used. If the model does not converge, then either the compound symmetry or autoregressive (whichever model has the lower AIC statistic) covariance matrix structure will be used instead. At this time point (up to 8 weeks) we do not expect a high proportion of dropouts, as a placebo effect of the sham treatment is expected and was taken into consideration in the design of the study. Thus, any missing data at 8 weeks post treatment initiation can be considered missing at random. Therefore, since repeated measures ANOVA is also an imputation method, for this evaluation no other method of imputation of missing data is considered beyond the model estimates. Nevertheless, should the missing at random assumption prove to be incorrect, a sensitivity analysis using other methods for data imputation mentioned in Section 7 may be performed.

Mock SAS code for the analysis:

```
Proc Mixed data=HDRS17;
  class visit group center subjectid;
  model change_HDRS17 = baseline_HDRS17 visit group visit*group;
  repeated / type=un subject=subjectid;
  lsmeans group*visit / pdiff cl;
  random center;
run;
```

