The principal statistical analysis will be a comparison between the treatment groups, derived from the visit by treatment group interaction term from the model. The adjusted mean change from baseline in HDRS-17 scores at 8 weeks post treatment initiation will be estimated from the model (LS Means) interaction term for each group, as well as the difference between the adjusted means, and will be presented together with 95% confidence intervals. The null hypothesis will be rejected in favor of the alternative hypothesis and the study deemed

successful if the p-value is <0.05 and the mean change HDRS-17 in the active group is higher than that of the sham group.

The primary analysis model uses likelihood-based inference that is valid under a missing at random assumption.

Cohen's D will be calculated and presented as well as a measure of the clinical effect size of the change from baseline HDRS-17 at week 8. An effect size can also be calculated using methods described in "Effect sizes for growth-modeling analysis for controlled clinical trial in the same metric as for classical analysis", *Psychol Methods*. 2009 March; 14(1): 43-53), where $ES = \text{difference between LSmeans} / \text{Pooled SD of baseline HDRS-17 score}$.

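### The primary model ties weeks 4 and 8 to one baseline HDRS-17 slope; a baseline-by-visit term would be a small, cheap safeguard for the deciding week-8 contrast

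*Protocol*

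**What the plan says.** The Protocol synopsis, Protocol 12.9.1 and SAP 11.5.1 describe the same model for change in HDRS-17. Its terms are "treatment group, visit, treatment group by visit interaction with Baseline HDRS 17 and center entered as covariates". Read quickly, that phrase could suggest an interaction with baseline. The SAP code removes the doubt: "model change_HDRS17 = baseline_HDRS17 visit group visit*group", with "repeated / type=un subject=subjectid". Baseline HDRS-17 has one main effect and no visit-specific term, and the SAP is the controlling document: "This SAP prevails when differences exist in descriptions or explanations provided in the protocol and the SAP".

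The only post-baseline visits in the double-blind phase are Visit 3 (week 4) and Visit 4 (week 8). Success rests on the week-8 group difference, "derived from the visit by treatment group interaction term from the model". On missing data the SAP states without qualification: "The primary analysis model uses likelihood-based inference that is valid under a missing at random assumption".

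SAP 11.4 and 11.5.1 allow prognostic covariates to be added to the model, but neither names a baseline-by-visit interaction.

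**The concern.** One slope serves two visits. If baseline severity predicts change differently at week 4 and at week 8, the shared slope is a compromise. Under unstructured covariance the compromise favours the less variable visit, which is probably week 4. The week-8 comparison is then adjusted with a slope that is not its own.

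Two things are at stake. The first is precision: a chance baseline imbalance is over- or under-corrected at week 8. The second is the missing-at-random claim. Likelihood inference is valid under missing at random only if the mean model is also right. If the slopes differ and the kind of subject who leaves early differs between arms, the model predicts the missing week-8 values with the wrong slope, by different amounts in each arm.

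**Working it through.** **The plan's own figure.** Protocol 12.4: "We use conservative estimates of a 3.3-point difference with a standard deviation of 6 points", so d = 3.3/6 = 0.55. The exact two-sample t calculation gives 79.3% power at 52 per arm and 80.1% at 53, which reproduces the stated 53 per arm. The normal approximation, used below for comparisons, gives Φ(0.55 × √(53/2) − 1.96) = Φ(2.831 − 1.960) = 80.8%.

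**Inputs from the documents.** Protocol 12.4 reports feasibility SDs of 4.2 (week 3) and 5.6 (week 6), rounded up to 5 and 6. They stand in here for the residual SDs at weeks 4 and 8.

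**Inputs assumed.** Visit correlation r 0.3-0.8, baseline SD 3-4, slope gaps of 0.1-0.3 in the main range (0.5 as an extreme). Center was left out of the calculations.

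**Step 1: where the shared slope lies.** With complete data it tends to w4·b4 + (1 − w4)·b8, where

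w4 = (s8² − r·s4·s8) / (s4² + s8² − 2·r·s4·s8).

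- SDs 5/6, r 0.3: (36 − 9)/(61 − 18) = 27/43 = 0.63
- SDs 5/6, r 0.6: (36 − 18)/(61 − 36) = 18/25 = 0.72
- SDs 5/6, r 0.8: (36 − 24)/(61 − 48) = 12/13 = 0.92
- SDs 4.2/5.6, r 0.3-0.8: 0.70 to 1.10
- Equal SDs: 0.50 for any r

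Example: b4 = −0.2, b8 = −0.5, SDs 5/6, r 0.6. The shared slope is 0.72 × (−0.2) + 0.28 × (−0.5) = −0.284, against a true week-8 slope of −0.5.

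**Step 2: precision with complete data.** Week-8 residual variance is multiplied by 1 + (w4 × gap × SDbase)² / s8².

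In the example with baseline SD 4: (0.72 × 0.3 × 4)² / 36 = 0.746/36 = 2.1%. Power becomes Φ(2.831/√1.021 − 1.96) = 80.0%, down from 80.8%.

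For gaps up to 0.3, baseline SD 3-4 and r 0.3-0.7, the inflation is 0.1-3.9%. At 3.9%, power is Φ(2.831/√1.039 − 1.96) = 79.3%, a loss of about 1.5 points. With equal slopes, the shared-slope model is as precise or slightly more so (ratio of standard errors 0.98-1.00 in simulation at 62 per arm).

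**Step 3: bias under drop-out.** I fitted the two-visit likelihood model to very large samples (400,000 per arm; SDs 5/6, r 0.6, true week-8 difference −3.30). Drop-out before week 8 was logistic in baseline, with log-odds 1 per baseline SD.

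| Drop-out before week 8 | Missing | Gap 0.2: shared / by visit | Gap 0.3: shared / by visit |
|---|---|---|---|
| None | 0% | −3.299 / −3.297 | −3.305 / −3.308 |
| Depends on baseline alike in both arms | about 18% | −3.312 / −3.313 | −3.331 / −3.331 |
| Depends on baseline in one arm only | about 16% | −3.180 / −3.295 | −3.139 / −3.314 |
| Opposite directions in the two arms | about 18% | −3.087 / −3.320 | −2.957 / −3.304 |

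The first two rows show no bias. In the last two the models differ by 3.295 − 3.180 = 0.12 up to 3.304 − 2.957 = 0.35. Over the other SD and r settings tried, gaps of 0.2-0.3 gave about 0.10 to 0.36. A gap of 0.5 with opposite drop-out reached about 0.6. Bias was toward zero here, but its direction depends on the signs assumed. With the by-visit term it was about zero throughout.

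**The case against.** The best case for leaving the model alone is that nothing in the documents shows the slopes differ. The SDs that tilt the shared slope come from weeks 3 and 6 of an uncontrolled feasibility study. A baseline main effect is a legitimate pre-specified choice, and randomisation supports the comparison. Eligibility requires HDRS-21 of at least 20, which truncates baseline severity and argues against a large baseline SD. All of this stands, and it keeps the point small.

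A reader might go further and infer that the estimate is biased whenever drop-out depends on baseline. The second row of the table contradicts that. Bias needs unequal slopes and, in addition, a link between baseline and drop-out that differs by arm. Protocol 12.4 assumes drop-out irrespective of study arm.

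A reader might also infer a serious loss of power. Simulations at 62 per arm with about 15% differential drop-out and stronger assumed slopes fall as low as 67%. They do not describe the principal set. mITT keeps only subjects who reached the minimal stimulation time, so few week-8 values should be missing. They may not be nil: 70% of 2400 minutes is 1680, and at 80 minutes on 5 days a week that takes 1680/400 = 4.2 weeks after the uncounted first week. A subject could therefore qualify and still miss week 8. Selection into mITT is a separate matter that this term does not address.

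Nor should the effect of chance imbalance be counted as a further harm on top of the variance increase. They are the same effect.

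On the other side, the plan itself treats these issues as live. SAP 11.4 relates baseline HDRS total to change at week 8 and again at week 4, and SAP 7 foresees examining drop-outs' baseline characteristics by arm.

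**Conclusion.** The point holds as a minor specification weakness. The model imposes one baseline slope on both visits, and with SDs that rise over time that slope is mainly the week-4 one. If the slopes differ by up to 0.3, the cost is about 0-4% of week-8 variance and at most about 1.5 power points. Bias of about 0.1-0.4 of 3.3 points arises only if drop-out also depends on baseline differently by arm with 16-18% missing. It should be smaller in mITT. The ITT sensitivity analysis is more exposed, because it keeps the subjects who left early.

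These sizes rest on an assumed baseline SD, slopes and visit correlation, and on week-3 and week-6 SDs used as proxies. The SAP's statement on missing at random needs the qualifier that the mean model must also be right.

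**What to change.** Add `baseline_HDRS17*visit` to the model statement in SAP 11.5.1, and name the baseline-by-visit interaction in the text there and in Protocol 12.9.1 and the synopsis. Handle center as the text describes. Evaluate the week-8 LS means at the overall mean baseline. Use the same form for the endpoints analysed with a similar model that have a baseline value: MADRS, QIDS-SR-16, CGI-S and HDRS-21. Qualify the missing-at-random sentence accordingly.

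The cost is one degree of freedom, a negligible loss of precision if the slopes are equal, and a wording change. No new data are needed. SAP 6 says the treatment code had not been revealed when the SAP was finalised. If that is still so, the term can be pre-specified, which is cleaner than adding it after the prognostic-factor screen. If the code has since been opened, report the model with the term as a supportive analysis.
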